#### **Statistical Analysis Plan:**

Since this is a preliminary trial that is not powered to show that mirtazapine is better than placebo in the treatment of anxiety in children and adolescents with PDD, we will analyze the data to determine whether the following pre-specified positive indicators of efficacy are present.

1. Significant improvement in PARS score with mirtazapine.
2. Proportion of subjects receiving mirtazapine rated as responders is 50% or greater.
3. Change in PARS score is numerically greater with mirtazapine than placebo.
4. Proportion of subjects rated as responders to mirtazapine is numerically greater than placebo.

Outcome measures will also be analyzed to determine whether there are statistically significant differences between mirtazapine and placebo. However, these will be considered exploratory since they may be underpowered.

The primary outcome measure, PARS score, and other continuous measures will be analyzed using a mixed effects linear model using PROC MIXED in SAS with a REPEATED statement. Prior to running analyses, each dependent variable will be checked for normality and transformed if necessary. In accordance with intention-to-treat principles, data from all subjects having at least one visit following baseline will be analyzed. Significant main effects will need to be significant at an alpha level of 0.05.

For the CGI-I rating, subjects classified as “much” or “very much improved” will be defined as **responders** and all other classifications will be regarded as non-responders. We will be using this classification of the subjects throughout the trial as the dependent variable in these analyses. Hence, the CGI-I dichotomous variable will be examined over the study using a model with time treated as a repeated factor and treatment group as a fixed effect.

The occurrence of particular adverse effects during the 10-week treatment period will be compared between groups using Chi-square tests. In addition to absolute measures, height, weight and body mass index will be transformed to standardized z scores using anthropometric indices based on the 2000 Centers for Disease Control and Prevention age- and gender-normed growth charts (<http://www.cdc.gov/growthcharts/>). These z scores will then be analyzed in a similar manner to those used for other continuous measures described above.

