### **Sample Size Consideration and Power Analysis:**

The baseline to endpoint comparisons of mirtazapine (n=20) have 80% power to detect an effect size of 0.7 (two-tailed significance of 0.05). The mirtazapine (n=20) vs. placebo (n=10) analyses of the secondary comparisons have 80% power to detect an effect size of 1.1.

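### Two of the four efficacy indicators have no placebo reference, the other two compare with placebo only numerically, and no rule says how the four combine

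*Combined protocol and SAP*

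**What the plan says.** The Statistical Analysis Plan states that the trial is preliminary and not powered to show superiority over placebo. It then lists four pre-specified indicators of efficacy:

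- Item 1: "Significant improvement in PARS score with mirtazapine".
- Item 2: "Proportion of subjects receiving mirtazapine rated as responders is 50% or greater".
- Item 3: "Change in PARS score is numerically greater with mirtazapine than placebo".
- Item 4: the responder proportion is numerically higher on mirtazapine than on placebo.

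The section Sample Size Consideration and Power Analysis confirms that item 1 is a within-arm test: "The baseline to endpoint comparisons of mirtazapine (n=20) have 80% power to detect an effect size of 0.7". The same section treats the placebo comparisons as secondary: "analyses of the secondary comparisons have 80% power to detect an effect size of 1.1".

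The plan will also test mirtazapine against placebo on the outcome measures, outside the list of four: "However, these will be considered exploratory since they may be underpowered". For responders, "the CGI-I dichotomous variable will be examined over the study using a model with time treated as a repeated factor", so no Week 10 comparison is singled out. The analysis set is given as "data from all subjects having at least one visit following baseline will be analyzed".

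Specific Aims (aim 2) says that the size of the placebo effect on anxiety in this population is not known. Study Design gives learning about that effect as the reason for the control arm.

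**The concern.** A baseline-to-endpoint change in one arm adds together drug effect, placebo response, natural course and any regression to the mean. Only the concurrent placebo arm can separate them, and items 1 and 2 do not use it. Items 3 and 4 do, but without a drug effect each is close to a coin toss.

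Because no combination rule is given, the plan does not say what follows if item 1 is met while placebo improves more, so that item 3 fails. An investigator following the plan could report a met efficacy indicator from an improvement that is not specific to the drug. The Specific Aims and Innovation sections present the trial as the step before a larger one and as support for its funding, so that decision could be misdirected.

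Regression to the mean may add to item 1, because entry requires a PARS of at least 10 and PARS is also the primary outcome. This depends on which visit sets eligibility. PARS is taken at both screening and baseline (Schedule of Measures), and the Inclusion Criteria do not say which counts. If eligibility rests on the screening value, the separate baseline measurement would remove much of the artefact.

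**Working it through.** **Inputs from the documents.** 20 mirtazapine and 10 placebo subjects; two-sided alpha 0.05; within-arm effect size 0.7 and between-arm effect size 1.1, each at 80% power (Sample Size Consideration and Power Analysis).

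**Assumed inputs.** The documents give no placebo response. The shared, non-specific PARS improvement is therefore taken as 0.3, 0.5 or 0.7 SD of the change score in both arms, with no drug effect. Shared responder rates are taken as 30% and 34.6%. The latter is the global CGI-I rate in the retrospective study (9 of 26), used only as an illustration because those patients were treated open-label and were mostly treatment-resistant.

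**1. The plan's own power figures.** Within-arm, paired t-test, 19 df, noncentrality d√20:

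- 80% power is reached at d = 0.66, which rounds to the stated 0.7. At exactly 0.7 the power is 84.4%.

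Between-arm, 28 df, noncentrality d/√(1/20 + 1/10):

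- At d = 1.1 the power is 78.3% by the t distribution and 81.1% by the normal approximation.

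Both are consistent with the text. There is no arithmetic error in the plan here.

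**2. Item 1 with no drug effect.** The same within-arm formula applies, with d now the shared improvement and significance counted only in the direction of improvement.

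| Shared improvement (SD of change) | 20 analysed | 18 analysed |
|---|---|---|
| 0.3 | 24.7% | 22.4% |
| 0.5 | 56.5% | 51.6% |
| 0.7 | 84.4% | 79.9% |

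With no shared improvement the rate is 2.5%. The paired t-test approximates the planned mixed model, whose within-arm contrast is not specified. The top row of the range is the plan's design effect size: the test responds equally to 0.7 SD from the drug and 0.7 SD from anything else.

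**3. Item 1 met while placebo does numerically better.** By simulation (400,000 trials, 20 vs 10, no drug effect): 5.3%, 19.2% and 37.1% at 0.3, 0.5 and 0.7 SD.

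**4. Item 2.** Exact binomial, P(X ≥ 10 of 20): 4.8% at a 30% response rate and 11.4% at 34.6%.

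**5. Items 3 and 4.** Item 3 is met 50% of the time by symmetry. Item 4, by exact enumeration of P(X₁/20 > X₂/10), is met about 45% of the time; ties account for the shortfall from 50%.

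**6. If all four had to be met.** By simulation, with an assumed correlation of 0.6 between PARS change and latent response, across 0.3 to 0.7 SD: 2.3–3.2% at 30% response and 4.4–6.9% at 34.6%. At 0.7 SD and 34.6%, varying the correlation from 0.3 to 0.8 gives 5.6–7.8%.

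**7. Precision of a between-arm readout.**

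- PARS, 95% CI half-width: t(0.975, 28) × √(1/20 + 1/10) = 2.048 × 0.387 = 0.79 SD, before any gain from adjusting for baseline.
- Responders, half-width 1.96 × √[p(1 − p)(1/20 + 1/10)]: 36 percentage points at p = 34.6% and 37 at p = 40%.
- Power (noncentral t, 28 df): 24% at d = 0.5 and 42% at d = 0.7.

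**The case against.** The strongest defence is disclosure. The plan says that it is a pilot without power against placebo, speaks of indicators rather than proof, includes two items that compare with placebo, and schedules between-arm tests. Nowhere does it say that item 1 alone shows a drug effect. A reader who sees item 1 met and item 3 failed could discount the first, and a pre-specified list makes selective reporting visible. All of this is true, and it makes this a matter of labelling and interpretation rather than a calculation error. It does not change what item 1 measures, and the plan leaves the mixed result without a stated reading. Low power is a reason to report an imprecise between-arm estimate, not to substitute an uncontrolled one.

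A second objection is that requiring all four items is strict. It is, at roughly 2–7% under the assumptions in step 6, but the plan does not require it.

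Three stronger readings are tempting and not supported:

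- That 25–84% is the false-positive rate of the trial's conclusion. It is the rate for one item, and the plan defines no overall decision.
- That item 1 is always the weakest item. At 0.3 SD it is met less often by chance than items 3 and 4; it overtakes both only between 0.4 and 0.5 SD.
- That regression to the mean certainly inflates item 1. That depends on the visit used for eligibility, which is not stated.

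**Conclusion.** The point holds as a cheap improvement that should be made. Items 1 and 2 are called indicators of efficacy without any reference to placebo, items 3 and 4 ask only for a numerical lead, and no combination rule is given. With no drug effect, item 1 alone is met about 25%, 56% or 84% of the time at 0.3, 0.5 or 0.7 SD of shared improvement (22–80% across that range if 18 are analysed), and in about 5%, 19% or 37% of trials it is met while placebo does better.

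The size rests on an assumed range, because the documents give no placebo response, and on SDs of the change score. If the same 0.3–0.7 is read on the baseline-SD scale, the range is unchanged at a baseline–endpoint correlation of 0.5, but becomes 19–71% at 0.3 and 38–97% at 0.7. The structural point does not depend on these figures.

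**What to change.** Replace the list in the Statistical Analysis Plan with wording such as:

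> The efficacy readout is the mirtazapine-minus-placebo difference at Week 10 in (a) PARS, from the mixed model with a treatment-by-visit term and a Week 10 contrast, adjusted for baseline PARS, and (b) the proportion of CGI-I responders. Each is reported with a 95% confidence interval and described as preliminary. Within-arm PARS change and responder proportion are reported with 95% confidence intervals for both arms as supportive description, not as indicators of efficacy.

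The placebo-arm summary also serves aim 2.

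If the list of four is kept, label items 1 and 2 supportive and state that no sign of efficacy is claimed unless items 3 and 4 also favour mirtazapine. This is the weaker option. At 30% shared response and a correlation of 0.7, items 1, 3 and 4 are still all met with no drug effect in about 13%, 24% and 30% of trials at 0.3, 0.5 and 0.7 SD.

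**Cost.** No extra patients, visits or data. The models do change: the plan states no baseline covariate and no Week 10 contrast, and its responder model covers the whole study. The main downside is imprecision, with half-widths of about 0.79 SD for PARS and 36–37 percentage points for responders. Power is about 24% at d = 0.5 and 42% at d = 0.7, so the readout will often be inconclusive.

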## **E. RESEARCH STRATEGY**

### **Study Design:**

A 10-week, flexibly-dosed, double-blind trial with 2:1 randomization to either mirtazapine or placebo was chosen as the optimal way of gathering quality preliminary data. Participants will be seen at screen, baseline (randomization), and following 2, 4, 6, and 10 weeks of treatment. The duration of the trial will allow us to adjust the dose of study drug over the first 6 weeks and allow for stable dosing during the final 4 weeks of the trial. Unbalanced randomization was chosen so that the majority of subjects will receive mirtazapine which will allow us to gather more information about the efficacy of mirtazapine in a broader range of subjects. A placebo control group will help us determine placebo effects in the treatment of anxiety in PDD.

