#### **Mirtazapine/Placebo Treatment:**

Subjects will receive 7.5 mg of mirtazapine nightly at the start of the trial. The dose will be increased by 7.5 mg per week for subjects with weights less than 50 kg and by 7.5 or 15 mg per week for subjects weight greater than 50 kg depending on efficacy and tolerability. During the first 6 weeks, patients will be seen bi-weekly with additional telephone visits conducted in between clinic visits for additional monitoring of adverse effects and for dosing adjustment as necessary. The optimal dose will be reached by week 6 of treatment. A final visit will be conducted at week 10 with a follow up phone call at week 8. The minimum starting dose will be 7.5 mg and the maximum total daily dose will be 45 mg (based on our preliminary study and clinical use). Medication will be dosed once or twice daily depending on response and tolerability. Our previous experience has found the addition of a morning dose to be well-tolerated and effective in a clinical sample (Posey et al 2001). Once daily dosing at night only will be allowed if children are unable to tolerate a morning dose due to sedation.

Matching placebo prepared by a compounding pharmacy will be identical to mirtazapine in appearance and taste.

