### **End of Trial Alternatives:**

At the completion of the 10-week trial, the prescribing physician will break the blind in order to decide on an appropriate next step for the participant. Placebo treated subjects still exhibiting clinically significant anxiety will be entered into a 10-week open-label trial of mirtazapine of similar design to the double-blind trial with the exception that the outcome measures will be more limited in scope and conducted by the physician. This will help to protect the blinded rater from gaining any knowledge that might influence their ratings during the course of the study. This mechanism has been used successfully in studies conducted by the RUPP Autism Network.

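### Do the two responder indicators need a written rule for a child with no Week-10 CGI-I rating?

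*Combined protocol and SAP*

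**What the plan says.** The Statistical Analysis Plan says the trial is not powered to show superiority over placebo, so it relies on four pre-specified indicators. The second is "Proportion of subjects receiving mirtazapine rated as responders is 50% or greater" and the fourth is "Proportion of subjects rated as responders to mirtazapine is numerically greater than placebo". A responder is a child rated 1 or 2 on the CGI-I; every other rating is a non-response. A rating that was never made is not mentioned.

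The analysis set is given in the paragraph on PARS and the other continuous measures: "In accordance with intention-to-treat principles, data from all subjects having at least one visit following baseline will be analyzed". For the responder variable, a later paragraph of the plan states that "the CGI-I dichotomous variable will be examined over the study using a model with time treated as a repeated factor and treatment group"; group is the fixed term. The plan does not tie that model to the two indicators.

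The visit has to be inferred. Study Design sets the dosing period so as to "allow for stable dosing during the final 4 weeks of the trial". The treatment section states "A final visit will be conducted at week 10 with a follow up phone call at week 8". The power section speaks of baseline-to-endpoint comparisons. The Schedule of Measures has CGI-I at Weeks 2, 4, 6 and 10 and lists no early-termination visit.

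**The concern.** Taking Week 10 as the visit does not fully settle the two indicators. A child seen at Week 2, 4 or 6 but not at Week 10 belongs to the stated analysis set and has no Week-10 rating. Such a child could be counted as a non-responder, given the last available rating, or left out of the proportion. In arms of 20 and 10 these choices can give opposite answers against a fixed 50% bar or in a bare numerical comparison.

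Two of the four signs of efficacy are exposed. In addition, at the end of each child's 10 weeks "the prescribing physician will break the blind in order to decide on an appropriate next step for the participant", and enrolment runs over three years. A rule chosen only at analysis might therefore be chosen when some allocations are known within the team.

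**Working it through.** **Inputs from the documents.** Arms of 20 and 10 (Sample Size Consideration and Power Analysis); bar of 50% (Statistical Analysis Plan); retrospective response of 9/26 = 34.6% (Preliminary Studies, Results).

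**Assumptions, because the documents give no figure.** Week-10 loss of 5%, 10% or 20%, unrelated to response; true mirtazapine response from 34.6% to 50%; placebo response of 40% where indicator 4 is illustrated.

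**The plan's own figures.** The plan states "The baseline to endpoint comparisons of mirtazapine (n=20) have 80% power to detect an effect size of 0.7". A paired t calculation gives 84.4% at 0.7; the effect detectable with 80% power is 0.66, which rounds to 0.7. For 20 against 10 at effect size 1.1, the noncentral t gives 78.3% against the stated 80%. Both agree within rounding of the effect size, and they confirm the arm sizes used here.

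**Indicator 2, by counting.** Let m be the number of missing Week-10 ratings on mirtazapine, r the observed responders, and l the missing children whose last rating was a response.

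- Missing as non-response: met if r/20 ≥ 0.5, so r ≥ 10.
- Observed cases: met if r/(20 − m) ≥ 0.5.
- Last rating carried forward: met if (r + l)/20 ≥ 0.5.

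The first two disagree when (20 − m)/2 ≤ r ≤ 9.

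| m | r at which they disagree | Example |
|---|---|---|
| 1 | none | 10 responders needed under either rule |
| 2 | 9 | 9/18 = 50%, 9/20 = 45% |
| 3 | 9 | 9/17 = 52.9%, 9/20 = 45% |
| 4 | 8, 9 | 8/16 = 50%, 8/20 = 40% |

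With carry-forward as a candidate, one missing rating is enough: r = 9 and l = 1 gives 10/20 against 9/20.

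At a true 50% response, the chance of disagreement is C(18,9)/2^18 = 0.185 for m = 2, and [C(16,8) + C(16,9)]/2^16 = 0.371 for m = 4.

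**Indicator 2, averaged over a binomial number missing.**

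| Missing | Disagreement, true response 34.6% to 50% | Bar met at true 50%: observed cases / missing as non-response |
|---|---|---|
| 5% | 2.0% to 5.2% | 55.0% / 49.8% |
| 10% | 4.9% to 13.8% | 54.7% / 40.9% |
| 20% | about 10% to 30.5% | 54.9% / 24.5% |

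**Gain from choosing the rule afterwards.** At a true 40% with 20% missing, observed cases meets the bar in 24.6% of trials, missing-as-non-response in 7.2%, and carry-forward in 14.2% or 24.5% (if 20% or 40% of leavers' last ratings were responses). Taking whichever rule succeeds gives 25.6% or 30.0%. Over the best single rule that is 25.6 − 24.6 = 1.0 point, or 30.0 − 24.6 = 5.4 points.

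**Indicator 4.** Let a and b be the numbers missing on mirtazapine and placebo, and s the placebo responders. Missing-as-non-response compares r/20 with s/10; observed cases compares r/(20 − a) with s/(10 − b). If a = 2b, the missing fractions are equal, both comparisons reduce to r > 2s, and the two rules cannot disagree. With unequal loss they can: for a = 3, b = 0, r = 7, s = 4, the first gives 35% against 40% and the second 7/17 = 41.2% against 40%. At assumed response of 50% and 40%, disagreement is 12% for (a, b) = (2, 0), 10% for (3, 1), 22% for (4, 0) and 0% for (2, 1).

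**The case for a change.** The best argument for a change is that the plan relies on these indicators precisely because it has no powered test. A fixed bar with 20 children can turn on one or two ratings, and a few sentences would close the gap without new data. The repeated-measures CGI-I model does not close it, since no text links that model to the indicators. It is true that no rule is written, and the disagreement rates are arithmetically right under their assumptions.

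The argument weakens in four places.

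- The larger figures need heavy loss. The only retention figure in the documents is 25 of 26 children completing at least 4 weeks, so 1/26 = 3.8% did not. It is retrospective and shorter than 10 weeks, so it does not settle the rate, but it lies nearest the 5% row.
- Keeping an early leaver in the analysis set does not oblige anyone to invent a Week-10 value. The planned model can use incomplete series and, with time as a factor, can yield a fitted Week-10 proportion for each arm.
- End of Trial Alternatives unblinds the prescribing physician and keeps the rater protected. It does not say that whoever sets the analysis rules is unblinded.
- The obvious replacement rules are not neutral. Counting missing as non-response is strict for a pilot screen, and requiring indicator 4 to hold under two rules would raise a bar that the plan sets as merely a numerical difference.

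**Conclusion.** No change is called for. The plan leaves a detail unwritten; it does not state a rule that misleads. A competent analyst would read the indicators at Week 10, give numerators and denominators, and note any missing ratings. With 30 children, a reader could then recompute the observed-case and non-response versions from the counts. The indicators are a descriptive screen in a trial that calls itself preliminary and treats its between-arm tests as exploratory, so no confirmatory error rate depends on the choice.

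The size depends on loss that the documents do not give. On indicator 2, the two simplest rules disagree in roughly 2-5% of trials at 5% missing, rising to about 10-31% at 20%. On indicator 4, they disagree only when the realised missing fractions differ between arms. These figures assume that missingness is unrelated to response. Choosing among the candidate rules is a fair trade-off between leniency and strictness, and the documents do not show one to be correct.

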### **Inclusion Criteria:**

1. **Age 5-17 years.**
2. **Diagnosis of autistic disorder, Asperger's disorder, or PDD NOS based on DSM-IV-TR criteria.** A final diagnostic determination will be made by a board-certified child and adolescent psychiatrist with experience in the diagnosis of PDDs based on clinical history, review of records, mental status exam, and a thorough review of the information obtained from the Autism Diagnostic Interview-Revised (Lord et al 1994) and other administered rating scales.
3. **Clinically significant anxiety as evidenced by a Pediatric Anxiety Rating Scale (PARS) score of 10 or greater (5-item scale).** The PARS (Research Units on Pediatric Psychopharmacology Anxiety Study Group 2002) was chosen as an inclusion criteria (and outcome measure) since it assesses severity across common anxiety disorders in children including generalized anxiety, social anxiety, separation anxiety, and transition-associated anxiety. In addition, it is an instrument that allows the clinician to incorporate both child and parent report into a final clinician-rated score for each item.
4. **Abbreviated IQ greater than 50 on the Stanford Binet 5th Edition.**

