#### **Outcome Measures:**

1. **PARS**. The PARS will be the primary outcome measure. It will be conducted at screening, baseline, and each follow-up visit.
2. **Screen for Childhood Anxiety Related Emotional Disorders (SCARED)**. The SCARED (Birmaher et al 1999) is a 41-item scale that includes both a child/self-report and parent-report form. It assesses symptoms of panic disorder, separation anxiety disorder, social phobia, and generalized anxiety disorder, as well as school avoidance. It will be conducted at baseline and each follow-up visit.
3. **Child and Adolescent Symptom Inventory (CASI) Anxiety Items**. These include 20 parent-rated items from the Child and Adolescent Symptom Inventory that has been administered to children with PDD in previous trials (Sukhodolsky et al 2008). It will be conducted at baseline and each follow-up visit
4. **Aberrant Behavior Checklist (ABC)**. The ABC is a 58-item questionnaire with 5 subscales derived by factor analysis: Irritability, Social Withdrawal, Stereotypy, Hyperactivity, and Inappropriate Speech (Aman et al., 1985). It has been extensively used in psychopharmacological studies of autism and assesses many symptoms that are either central to autism (Social Withdrawal, Stereotypy, Inappropriate Speech) or

frequently a target of treatment (Irritability). It will be conducted at baseline and each follow-up visit.

5. **Children's Sleep Habit Questionnaire (CSHQ).** The CSHQ (Owens et al 2000) is a 46-item parent-report questionnaire that assesses bedtime resistance, sleep onset delay, sleep duration, sleep anxiety, night waking, parasomnia, sleep disordered breathing, and daytime sleepiness that has been used in children with PDD (Honomichl et al 2002). It will be conducted at baseline and each follow-up visit.

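### Indicator 3 rests on the sign of the between-arm difference in PARS change, and the plan gives baseline PARS no role in its model; a baseline-adjusted Week-10 contrast would be a small, cheap improvement

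*Combined protocol and SAP*

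**What the plan says.** The Statistical Analysis Plan states that the trial is not powered for superiority and lists four pre-specified indicators of efficacy. The third is "Change in PARS score is numerically greater with mirtazapine than placebo". It has no threshold, interval or test, and no visit is named. It is the only indicator that compares PARS, the primary outcome, between arms: the first is within the mirtazapine arm, and the second and fourth concern responder proportions.

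PARS and the other continuous measures "will be analyzed using a mixed effects linear model using PROC MIXED in SAS with a REPEATED statement". The section does not say whether baseline PARS is a covariate, one of the repeated responses, or used only by subtraction. Significance tests between arms are planned as well: "However, these will be considered exploratory since they may be underpowered".

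Baseline PARS will be available. Outcome Measures says of the PARS: "It will be conducted at screening, baseline, and each follow-up visit", and the Schedule of Measures agrees. Entry requires a "Pediatric Anxiety Rating Scale (PARS) score of 10 or greater (5-item scale"). Study Design describes 2:1 randomisation and mentions no stratification by PARS.

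**The concern.** In a trial of 30 children the arms can easily start at different PARS levels. Raw change subtracts the whole baseline difference, which is the right amount only if a one-point difference at baseline carries forward as one point at Week 10. If less carries forward, raw change favours whichever arm started higher. A baseline-adjusted contrast subtracts the amount that the data support.

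For an indicator that goes by sign alone, the two contrasts can point in opposite directions in the same trial. At stake is how one of four pilot indicators is read, and so part of the case for a larger trial. No confirmatory claim depends on it.

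**Working it through.** **The plan's own figure.** Sample Size Consideration and Power Analysis says that "The mirtazapine (n=20) vs. placebo (n=10) analyses of the secondary comparisons" have 80% power at an effect size of 1.1. With SE = sqrt(1/20 + 1/10) = 0.387 and two-sided 0.05 (two-tailed is stated for the within-arm comparison and assumed here), the normal approximation gives Phi(1.1/0.387 - 1.96) = 81.1%. The noncentral t with 28 df gives 78.3%. The stated figure reproduces, with no baseline adjustment in it.

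**Inputs.** From the documents: 20 versus 10 children, the sign rule, and baseline PARS collected. Assumed, because the documents give neither: baseline to Week-10 correlation rho = 0.3, 0.5 or 0.7, and ratio r of Week-10 SD to baseline SD = 1, 1.25 or 1.5. Ratios above 1 are included because the entry threshold restricts baseline PARS from below. Effects and imbalances are in baseline SDs. All 30 children are taken to reach Week 10.

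**Chance imbalance.** The SE of the baseline difference is 0.387 SD. A difference of at least 0.5 SD in either direction has probability 2 x P(Z > 0.5/0.387) = 19.7%.

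**Formulas.**
- Slope of Week-10 on baseline: b = r x rho.
- Variance factor for raw change: 1 + r^2 - 2 r rho.
- Variance factor for the adjusted contrast: r^2 (1 - rho^2) x 27/26, where 27/26 is the price of estimating a slope.
- Chance that raw change meets indicator 3 with no drug effect, given that mirtazapine starts d higher: Phi(d(1 - b) / (0.387 r sqrt(1 - rho^2))). The adjusted contrast gives 50%.
- Chance of a correct sign on raw change at a true 0.5 SD effect: Phi(0.5 / (0.387 x sqrt(variance factor))). The adjusted column is simulated with an estimated slope, 200,000 trials per cell.

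Example, r = 1 and rho = 0.5: b = 0.5. With d = 0.5 the chance on raw change is Phi(0.25/0.335) = 77%. The variance factors are 1.000 and 0.75 x 27/26 = 0.779, a cut of 22%.

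| r | rho | b | Variance cut from adjusting | Met on raw change, no effect, d = +0.5 | Correct sign, raw change | Correct sign, adjusted |
|---|---|---|---|---|---|---|
| 1 | 0.3 | 0.30 | 32.5% | 83% | 86.2% | 90.7% |
| 1 | 0.5 | 0.50 | 22.1% | 77% | 90.2% | 92.9% |
| 1 | 0.7 | 0.70 | 11.7% | 71% | 95.2% | 96.3% |
| 1.25 | 0.3 | 0.375 | 18.5% | 75% | 83.1% | 85.7% |
| 1.25 | 0.5 | 0.625 | 7.3% | 67% | 87.0% | 88.0% |
| 1.25 | 0.7 | 0.875 | -1.8% | 57% | 92.4% | 92.2% |
| 1.5 | 0.3 | 0.45 | 9.5% | 69% | 80.0% | 81.3% |
| 1.5 | 0.5 | 0.75 | -0.1% | 60% | 83.5% | 83.6% |
| 1.5 | 0.7 | 1.05 | -3.6% | 48% | 88.6% | 88.3% |

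If mirtazapine starts 0.5 SD lower, the fifth column becomes its complement. The variance loss is greatest at b = 1, where it is 1/26 = 3.8%. The change in the chance of a correct sign runs from -0.3 to +4.5 points.

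**Opposite signs.** In the same simulations, with no effect, the two contrasts disagree in 20/17/13% of trials at r = 1 (rho 0.3/0.5/0.7), 15/11/6% at 1.25 and 12/7/5% at 1.5. With a true 0.5 SD effect they disagree in 2 to 10%.

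**Why the slope must be free by visit.** These figures are for a Week-10 regression on baseline. A repeated-measures model with visit-specific slopes and unstructured covariance gives the same Week-10 contrast when data are complete. One slope shared by Weeks 2, 4, 6 and 10 does not, because baseline usually correlates more strongly with early visits. Take equal SDs, no effect and d = +0.5, with assumed baseline correlations at the four visits of 0.7/0.6/0.5/0.3. The average slope is 0.525 against 0.3 at Week 10, so the indicator is met with probability Phi(0.5 x 0.225 / (0.387 x sqrt(0.91))) = 62%. Correlations of 0.8/0.7/0.6/0.5 give 59%, and 0.8/0.75/0.72/0.7 give 53%. A fitted model weights the visits by their covariance and need not use the simple average; the range across these settings is then about 53 to 72%, against 50% with a visit-specific slope.

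**The case against.** The strongest reply is that the indicator is clear enough: change, compared numerically, means observed change, so baseline enters by subtraction. That is the most natural reading, and it stands. The opposite-sign rates therefore mainly compare the plan's ordinary reading with another estimator. What is unstated is the visit, whether the value is raw or model-based, and the place of baseline in the PROC MIXED analysis.

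It is also fair that the trial is a declared pilot, that between-arm tests are exploratory, and that the size of the gain rests on assumed correlations and SD ratios. In three of the nine settings adjustment slightly increases variance, and the entry threshold makes the less favourable settings plausible.

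A reader might infer more than the documents support:
- That raw change biases the comparison. It does not: it is unbiased over randomisation, and the dependence is on the imbalance in the particular trial.
- That the 5 to 20% disagreement with no effect is an error rate. It is not: with no effect neither sign is correct, and both contrasts pass half the time.
- That adjustment gives indicator 3 error control. A sign rule has none either way.
- That the planned model leaves baseline out. The text is silent; it does not exclude it.

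**Conclusion.** The point holds as a minor improvement. Indicator 3 is a sign rule on PARS change, and the plan gives baseline PARS no stated role in the model although it is collected. With 20 versus 10 children the sign of raw change in the realised trial depends on chance imbalance unless the Week-10 on baseline slope is near 1.

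For correlations of 0.3 to 0.7, adjustment cuts variance by 12 to 32% at equal SDs. At SD ratios of 1.25 to 1.5 it ranges from a 19% cut to a loss of about 4%. The chance of a correct sign at a true 0.5 SD effect changes by about -1 to +5 points. All of this rests on the assumed correlations and SD ratios and on complete Week-10 data. The better reason to act is that the contrast deciding a pre-specified indicator would be fixed before any baseline imbalance is seen.

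**What to change.** In the Statistical Analysis Plan, state one model for PARS:
- Response: PARS at Weeks 2, 4, 6 and 10 as the repeated measure, with unstructured covariance if it can be fitted.
- Terms: treatment, visit, treatment-by-visit, PARS at the baseline visit (not screening), and baseline-by-visit, so that the slope is common to the arms but free to differ by visit.
- Indicator 3: the sign of the adjusted Week-10 mirtazapine minus placebo difference (negative favours mirtazapine), reported with its confidence interval.
- Indicator 1: unchanged, as the within-mirtazapine baseline-to-endpoint comparison.

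The cost is a few sentences and four slope parameters, where a single shared slope would need one. No new data, visits or participants are needed. If Week-10 PARS proves much more variable than baseline PARS, up to about 4% of variance may be lost.
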